16.6.9 Aim 6 Expected Output

The expected output from Objective 1 is a classification rule for each major phenotyping task for which ≥ 460 overall patients are available. These classification rules can be immediately applied to future patient populations for future trials.

The expected output from Objective 2 is a suite of simulated trials of repurposed and/or hypothetical novel therapies. These trials would be used to motivate and to design next-generation trials in ARDS, pneumonia, and sepsis.

16.7.1 Aim 7 Background and Rationale

Multiple organ dysfunction syndrome (MODS) is a life-threatening disruption of organismal homeostasis. MODS is the hallmark of sepsis, is extremely common in ARDS, and is frequently present in pneumonia treated with respiratory support. In health, organs maintain their own homeostasis and communicate with other organs to maintain organismal homeostasis, a phenomenon termed crosstalk. The physiology of MODS is highly complex, in terms of the range of initial organs affected, disruptions in crosstalk pathways, and the pattern of organ dysfunction. In its terminal stages, MODS appears to be a final common pathway of a fatal insult; prior to those terminal stages, however, MODS may be a diverse syndrome. By convention, MODS in critically ill populations has been graded in terms of severity, using one of several scoring systems, e.g., the Sequential Organ Failure Assessment (SOFA).¹ Prior work in sepsis-related organ dysfunction has suggested various phenotypes that differ in clinical presentation and possible treatment effect heterogeneity in prior sepsis trials.² While these clinical phenotyping efforts provide preliminary evidence supporting the existence of phenotyping, deep phenotyping of MODS has not yet occurred. This Appendix seeks to determine whether deep phenotyping will identify distinct phenotypes within MODS.

16.7.2 Aim 7 Study Objectives

Primary Objective (Aim 7):

To determine whether the pattern of multiple organ dysfunction syndrome (MODS) differs by APS-identified phenotypes, using dimension reduction techniques to summarize the baseline Sequential Organ Failure Assessment (SOFA) scores, the most common clinical measure of MODS.

Exploratory Objectives (Aim 7):

1. Explore associations among constituent biomarkers (i.e., those used to define the APS phenotypes) and SOFA sub-scores at baseline.
2. Explore evolution of MODS over time, including its interaction with longitudinal phenotypes.
3. Explore the implications of alternative definitions of organ dysfunction (e.g., incorporation of lactate levels into cardiovascular sub-score, alternative methods of central nervous system dysfunction, relevance of specific biomarkers to organ failure definition)

16.7.3 Aim 7 Study Population

All APS Phenotypes Consortium Cohort Patients (N=4000)

16.7.4 Aim 7 Study Design

Broadly, dimension reduction techniques will be used to compare the distribution of organ dysfunction among the phenotypes identified within the APS Cohort.

16.7.5 Aim 7 Study Procedures

No additional laboratory procedures will be performed for this Aim. Procedures for this Aim are statistical and are outlined below. SOFA subscores will be calculated from clinically available results.

16.7.6 Aim 7 Data, Images, and Biospecimens Used from the APS Consortium

All available data results will be available for the underlying phenotyping. For the definition of MODS, daily SOFA scores will be utilized. (Based on previous analyses, last observation carried forward (LOCF) imputation will be employed for SOFA subscore constituents that are not obtained clinically.)

16.7.7 Aim 7 Statistical Analysis

The analysis for Aim 7 will follow principles of reproducibility and validation laid out on the protocol. There are two aspects of the proposed analysis: first is to use a dimension reduction technique such as PCA on the components of the SOFA score. This is expected to generate interpretable principal components reflecting combinations of organ dysfunction. Additional variables reflecting organ-specific functionality may be included in the analysis to fully capture dysfunction. Then, the principal components can be compared among *de novo* phenotypes to determine whether MODS differs among both previously derived and novel phenotypes. Comparison among phenotypes can utilize multiple group rank-based statistics (e.g., Wilcoxon rank sum) or regression modeling.

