described for plasma. For both plasma and respiratory sample data, metagenomics-identified pathogens will be compared with clinical microbiologic data and identified clinical pathogens.

For microbiome analysis, pre-processing steps will use *mothur*, *R*, and *vegan*, or comparable packages. Informed by published studies and preliminary data, for each specimen, we will derive key community features for analysis, such as: 1) bacterial density (quantified via ddPCR); 2) bacterial diversity (calculated using the Shannon Diversity index); and 3) community composition (using PERMANOVA analysis of beta-diversity and relative abundance of key bacterial taxa).

Comparative analyses for Aim 1a will compare features between previously derived LCA-defined phenotypes to test for enrichment of bacteremia, specific pathogens, or categories of pathogens (e.g., gram-positive or gram-negative bacteria) in a particular phenotype. In respiratory samples, we expect a more complex microbial community, including both airway commensals and potential pathogens so phenotypes may be compared using more global assessments of the microbiome, such as Bray-Curtis dissimilarity at the genus level as well as the Shannon diversity index.

For Aim 1b, we will incorporate data derived from whole blood host gene expression (Aim 2) in addition to the data described in this Aim. We will apply unsupervised analysis to the high-dimensional data (including whole-blood host gene expression, ETA host gene expression, ETA and plasma microbial composition) to characterize and interpret biological variation in the cohort. For host gene expression, we may perform principal component analysis (PCA) of gene counts following variance stabilizing transformation and selection of the top 1000 (or top 5000) most variable genes. Principal components representing >5% of total variance then enter the permutation-based jackstraw method to assign statistical significance to the association of individual genes with each principal component (or combinations thereof). The resulting gene loadings and p-values can then serve as input to functional/pathway enrichment methods, such as gene set enrichment analysis and IPA, in a manner analogous to traditional differential expression analysis, to facilitate biological interpretation. Canonical correlation analysis can then be used to characterize co-variation of biological features between the assayed compartments, namely blood and the lower airway.

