To harness all the high-dimensional data types for generating novel phenotypes, one approach we may use is to apply variance stabilizing transformation to count-based features, or log transformation for other continuous measurements, such as abundance of pathogens detected in mNGS. Then, reduced representations of high-dimensional data can be generated using linear combinations of the most variable original features derived from PCA. Principal components representing >5% of total data type variance might then be included in the reduced representation. Reduced datasets are then concatenated and can be clustered using the K-means algorithm. The optimal number of clusters can be determined using metrics of clustering quality, such as within cluster sums of squares, silhouette score, and gap statistics.

Once novel clusters have been established, we can compare the new clusters and LCA classes based on the maximum overlap and assess the similarity between novel cluster labels and LCA labels using the adjusted Rand index. The prognostic value of the new cluster labels and LCA labels can then be assessed for various outcomes, including mortality. Of particular interest when comparing methods is samples

allocated to different classes by different methods. Data types and features driving class discordance can be highly informative. Once novel clusters are established and validated, associations of clusters with various pathogen and microbiome features will be assessed similarly to Aim 1a.

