16.3.7 Aim 3 Statistical Analysis

As with all aims, the final statistical analysis plan will be fixed and filed prior to conducting the analysis. Here, we describe one potential approach for this aim, which will either be confirmed and fleshed out or updated with new methods available at the time of analysis. The primary analysis will include all enrollees to determine if there are latent respiratory phenotypes that are common to all critically ill patients; mechanically ventilated patients enrolled in the APS study will include patients intubated for pneumonia, sepsis, ARDS, and other causes of acute respiratory failure. Secondary analyses will focus within subgroups of patients who have been clinically phenotyped as having sepsis (both pulmonary and non-pulmonary), ARDS, and pneumonia. Some patients will be classified into more than one subgroup.

To approach this aim, a *de novo* latent class analysis (LCA) using previously described methods might be proposed.² For the primary analysis, clinical and respiratory variables along with HME biomarkers measured on the first day of mechanical ventilation would be considered. These variables include protein biomarkers (IL-6, IL-8, TNFR1, MCP1, RAGE, SP-D, Angiopoietin-2, ICAM-1, procollagen peptide-3, protein C, PAI-1 and total protein) along with age, sex, etiology of acute respiratory failure, PaO₂/FiO₂, PEEP, static compliance of the respiratory system, ventilatory ratio,¹⁰ and RALE score.¹¹ Respiratory and HME biomarker data available at a later timepoints for patients who are still intubated may be included in the analysis to determine whether phenotypes identified at the onset of ARF are stable over time and whether new respiratory phenotypes emerge in those who remain in ARF. Once we have determined whether latent respiratory phenotypes are present, we will investigate phenotype generalizability and stability, and test associations between respiratory phenotypes and pre-illness factors such as air pollutant exposure and socioeconomic factors.

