The variables used to perform LCA will be similar to those used in our prior studies and include clinical variables and protein biomarkers. Non-normally distributed data will be log-transformed and continuous variables will be scaled using z-scoring using values specific to the study day. Outcome data and severity scores (e.g., APACHE and SOFA scores) will be excluded from the modelling. We will build a minimum of five models, comprising of 1 to 5 classes respectively. We will use fit statistics and the Vuong-Lo-Mendall-Rubin test to determine the best fitting model in each cohort at each timepoint. Once identified, we will use the highest probability generated by the best fitting model to assign class membership. We will use latent transition modelling to evaluate the temporal stability of the classes at sequential time points. To establish overlap with the baseline molecular phenotypes, we will use the parsimonious classifier models comprising of IL-8, protein C, and serum bicarbonate. We plan to use a probability of ≥ 0.5 to assign molecular phenotypes. We will perform mixed effect modeling assessing for overall group differences in parsimonious model probabilities over time between survivorship groups in each phenotype independently. We will perform unadjusted (main) and confounder-adjusted analysis of probabilities trajectories, to ascertain cluster association with outcomes.

For gene-based existing phenotypes, we will use repeated RNA-sequencing data to classify patients to the various phenotypes (SRS, MARS, etc.). We will use the probabilities of belonging to the phenotypes on each day to model for trajectories and use outcome data to evaluate the prognostic value of the changing probabilities and switching of phenotypes, adjusting the models for treatment such as corticosteroids.

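### Aim 7 does not keep SOFA inputs out of the novel phenotypes it then compares on SOFA, and exploratory Aim 1b tests clusters on features of the kind that formed them

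*Protocol*

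**What the plan says.** **Aim 7.** The primary objective (Protocol 16.7.2) is "To determine whether the pattern of multiple organ dysfunction syndrome (MODS) differs by APS-identified phenotypes", using baseline SOFA. The population (16.7.3) is the whole cohort of 4,000. On inputs, 16.7.6 states: "All available data results will be available for the underlying phenotyping". Section 16.7.7 reduces the SOFA components by a method such as PCA, allows further organ-function variables into that step, and compares the resulting components between phenotypes "to determine whether MODS differs among both previously derived and novel phenotypes". No sentence separates the variables that build a phenotype from those it is compared on.

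**Where the phenotypes come from.**
- Aim 3 (16.3.7) proposes a latent class model on airway biomarkers "along with age, sex, etiology of acute respiratory failure". The list goes on to PaO2/FiO2, and section 7.2.2 ties respiratory SOFA dysfunction to that ratio.
- Aim 4 (16.4.7.1) says: "Outcome data and severity scores (e.g., APACHE and SOFA scores) will be excluded from the modelling". It does not mention the raw constituents of those scores. Section 16.4.7.2 carries the same procedures and features into the novel longitudinal classes.
- The classifier for the existing hyper- and hypoinflammatory phenotypes uses IL-8, protein C and serum bicarbonate (16.4.7.1).

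**Aim 1b.** Section 16.1.7 lists the inputs to the unsupervised analysis as including "ETA host gene expression, ETA and plasma microbial composition". It then says that, once clusters are established and validated, "associations of clusters with various pathogen and microbiome features will be assessed similarly to Aim 1a". Aim 1a is described there as testing for enrichment.

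**General safeguards.** Section 12.2.4 asks for validation of stability and of predictive information. Section 12.2.5 advises considering a run of any multi-phase procedure on pure-noise data, decided SAP by SAP.

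**The concern.** A clustering algorithm picks labels that spread the clusters apart on its own inputs. A rank test or regression then treats those labels as if they had been assigned without sight of the values. When the tested variable was an input, that assumption fails and the p-value is too small.

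Aim 7's primary question is whether the pattern of organ dysfunction differs by phenotype. If a novel phenotype was partly built from P:F ratio, or from any other SOFA constituent, part of a positive answer is built in. Section 16.7.9 already expects relevant differences, so such a result would probably be read as confirmation. The stability checks in section 12.2.4 would not reveal it, because a difference created by construction can be perfectly stable. Aim 1b has the same structure, with microbial features in place of SOFA.

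**Working it through.** **1. The plan's own figure.** Section 16.7.8 gives a half-width of about 0.1 to 0.2 for an odds ratio of 0.8. With half-width = OR × 1.96 × sqrt[1/(n1·p1·(1−p1)) + 1/(n2·p2·(1−p2))] and n = 4,000 (group shares and event rates assumed):
- Equal groups, 50% reference rate: p1 = 0.8/1.8 = 0.444; SE = sqrt(0.002025 + 0.002000) = 0.0634; half-width = 0.8 × 1.96 × 0.0634 = 0.10.
- 25:75 split, 10% reference rate: p1 = 0.0816; SE = sqrt(0.01334 + 0.00370) = 0.1306; half-width = 0.8 × 1.96 × 0.1306 = 0.20.

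The stated range is reproduced and is not in dispute. It describes precision for groups taken as given and says nothing about groups formed from the tested variable.

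**2. Null simulation for Aim 7.** There were six independent SOFA-like sub-scores (0 to 4) and independent normal noise features. All inputs were standardised, followed by k-means with k = 3, PCA of the six sub-scores, and Kruskal-Wallis between clusters. The protocol sets no alpha here; 5% was assumed. Nothing is truly associated, so the correct rejection rate is 5%.

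| n | Clustering inputs | of which SOFA | PC1 at 0.05 | Any of PC1–3 at 0.05/3 | Runs |
|---|---|---|---|---|---|
| 4,000 | 20 | 6 | 100% | 100% | 200 |
| 4,000 | 20 | 1 | 88% | 96% | 200 |
| 4,000 | 50 | 6 | 98% | 100% | 100 |
| 4,000 | 150 | 6 | 93% | 100% | 60 |
| 1,500 | 150 | 6 | 86% | 99% | 100 |
| 4,000 | 14 | 0 | 4% | 5% | 300 |
| 4,000 | 144 | 0 | 3% | 5% | 60 |

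The 150-feature rows use the count in section 16.4.8. A smaller set-up (n = 1,500, ten inputs, one of them SOFA) gave 86% and, in a separate run, 90% on the PC1–3 criterion. Monte Carlo error does not change the reading: for 93% in 60 runs, SE = sqrt(0.93 × 0.07/60) = 3 points.

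**3. Null simulation for Aim 1b.** With n = 1,500, ten host features, five microbial features and k = 3, a test of one microbial feature rejected in 94.5% of runs when the microbial features were clustered on and in 5.3% when they were not.

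**4. When real clusters exist.** The noise case is the extreme, so the test was repeated with true clusters in the nine other inputs and one null SOFA input (n = 1,500, k = 3, PC1–3 criterion). Two set-ups gave:

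| Distance between centres | Rejection |
|---|---|
| 1 SD | 90% (one set-up only) |
| 2 SD | 49% and 66% |
| 3 SD | 10% and 16% |
| 4 SD | near nominal in both (5% in one) |

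With SOFA left out of the inputs, rejection was 3% to 6%. The middle rows depend on how the centres are laid out. The pattern does not: inflation is large when the shared variable helps decide membership and vanishes when the other inputs already settle it.

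**The case against.** The strongest reply is that nothing here is fixed. Section 16.7.6 makes data available without requiring their use. Aim 3's model is one potential approach, Aim 1b's methods are offered as an example for an exploratory objective, and every analysis is to have its own SAP, which is not at hand. Feature lists normally belong there. That stands against calling Aim 7 circular outright. It does not remove the point, because the described sequence, followed as written, produces the overlap and no binding sentence prevents it.

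The noise simulations also force three clusters, whereas the protocol would select the number by fit statistics, silhouette or gap. In a check on ten noise inputs, the gap statistic chose one cluster in 30 of 30 runs and mixture-model BIC chose one class in 20 of 20, so no comparison would follow. This is a fair limit on the noise figures. The weak-separation results in step 4 are the relevant ones, and they remain inflated. Section 16.4.8 reports well-separated classes in prior work; if that held for the novel phenotypes, the inflation would be small.

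The one documented overlap, P:F in Aim 3, concerns about 1,500 ventilated patients on their first day of ventilation, while Aim 7 uses baseline SOFA in 4,000. The overlap is therefore partial.

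Section 12.2.5's noise-data run would expose the problem, but it is advisory and neither aim specifically commits to it.

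A reader might also infer that Aim 4's classes contain platelets, bilirubin, creatinine or vasopressors. The protocol does not list them as inputs. It excludes the scores and is silent on the constituents.

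**Conclusion.** The point holds in limited form. Aim 7 is open to circularity for novel phenotypes, and Aim 1b as described contains it for whichever tested features were also clustering inputs. P-values on shared features are anti-conservative: about 85% to 100% rejection at a nominal 5% when clusters are absent or barely separated, falling to nominal at about 4 SD with one shared input. With no shared input the rate is 3% to 6%.

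A reader might infer that Aim 7 would find a difference almost regardless of biology. The documents do not support that: no novel phenotype's inputs are fixed, Aim 4 keeps severity scores out, and well-separated clusters show little inflation. Nor does the problem extend to the IL-8, protein C and bicarbonate classifier, which has no SOFA input, although the comparison sentence in 16.7.7 covers previously derived phenotypes too.

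The rates rest on independent variables, k-means with k = 3 and assumed feature counts. The direction does not depend on those choices; the size does.

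**What to change.** - **Aim 7:** keep the APS phenotypes as derived. For each one, drop from the inferential SOFA comparison every sub-score whose inputs entered that phenotype, and report those sub-scores descriptively without p-values. Apply the same rule to any further organ-function variables added to the dimension reduction. A phenotype version derived without SOFA inputs can serve as a sensitivity analysis. It should not replace the primary phenotypes, because the objective asks about the phenotypes the consortium identifies.
- **Aim 1b:** test clusters only on features not used to form them, and report the clustering features descriptively.
- **Both:** make the noise-data simulation of section 12.2.5 mandatory, including the step that chooses the number of clusters.

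This extends the exclusion Aim 4 already applies to severity scores. The cost is SAP wording, some extra analysis, and fewer sub-scores formally tested for some phenotypes. No data collection changes.

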16.7.8 Aim 7 Adequacy of sample size

As indicated in the master protocol, there is no clear method for establishing precise sample sizes for unsupervised analyses such as clustering. We have shown in the rationale for the cohort sample size that group sizes of 2000 or more sufficient for identifying clusters when using 500 features or more. For comparison among phenotypes, we have shown that a small effect such as an odds ratio of 0.8 can be estimated with a half width of the confidence interval ranging from about 0.1 to 0.2 under the full range of assumptions.

16.7.9 Aim 7 Expected Output

It is expected that this Appendix will identify relevant differences in the distribution of organ failure among the APS phenotypes. It is anticipated that this will further illuminate the possibility of phenotypes that span the historic syndromes of ARDS, pneumonia, and sepsis.

